1. INFORMATION FROM THE STUDY PROTOCOL

1.1. Introduction and Objectives

1.1.1. Introduction

This document presents the statistical analysis plan (SAP) for Study RM-493-023, A Phase 3 trial of Setmelanotide (RM-493), a Melanocortin-4 Receptor (MC4R) Agonist, in Bardet-Biedl Syndrome (BBS) and Alström syndrome (AS) Patients with Moderate to Severe Obesity. This SAP is based upon protocol version dated 26 August 2020.

This SAP is designed to outline the methods to be used in the analysis of study data in order to answer the study objectives. Populations for analysis, data handling rules, statistical methods, and formats for data presentation are provided. The statistical analyses and summary tabulations described in this SAP will provide the basis for the results sections of the clinical study report (CSR) for this study.

In addition, the SAP is intended to clarify many of the details of the more limited discussion in the statistical section of the protocol, therefore, the SAP will expand on and may modify the plans outlined in the study protocol. If changes are made to the plans outlined in the protocol, the SAP will supersede the relevant contents of the protocol. If, after the study has completed, changes are made to the SAP, then these deviations to the plan will be listed, along with an explanation as to why they occurred, in the Clinical Study Report for the study as appropriate. It should be noted that a cohort of the supplemental patients was added into the protocol in the midcourse of the study. However, the sponsor has specified that the patients categorized in the pivotal cohort include all the enrolled BBS/AS patients at the time of the planned sixth AS patient enrollment. Based on this definition, and up to the finalization of the SAP, it is concluded that a total of 38 patients (the first 32 BBS patients and 6 AS patients) will make up the pivotal cohort. The full list of pivotal cohort patients is provided in Appendix I. All analyses for CSR and Submission, including demographics, disposition, baseline characteristics, efficacy, and safety etc., will be performed and the conclusions will be drawn based on the data from the pivotal cohort of patients. The purpose of the supplemental cohort is to gain more treatment experience. Therefore, unless stated otherwise, all analyses in the SAP refer to pivotal cohort only.

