2. ANALYSIS POPULATION

2.1. Population Definitions

The following analysis populations will be evaluated and used for presentation and analysis of the data.

- Screening Analysis Set: All patients who signed the informed consent form.
- Safety Analysis (SA) Set: All patients who received at least 1 dose of study drug (placebo or setmelanotide). Analysis performed on the safety set will be based on patients according to treatment received.
- FAS: All patients (irrespective of age) who received at least 1 dose of setmelanotide and have baseline data.
- DUS: All patients in the FAS who demonstrate at least 5 kg weight loss (or at least 5% if baseline body weight is < 100 kg) over the first 14 weeks of active setmelanotide treatment, regardless of later disposition.

For any DUS analysis, the DUS subgroup includes:

- O Those patients initially randomized into the setmelanotide group in the double blinded, randomized, placebo-controlled period that achieved at least 5 kg weight loss (or at least 5% if baseline body weight is < 100 kg) from baseline at Week 15 visit.
- O Those patients who initially randomized in the placebo group in the double blinded, randomized, placebo-controlled period, and achieved at least 5 kg weight loss (or at least 5% if baseline body weight is < 100 kg) from week 15 (i.e., just prior to their first active dose of setmelanotide at week 15) through week 29 (i.e., after 14 weeks of active treatment with setmelanotide).
- PCS: All randomized patients who received at least 1 dose of placebo or setmelanotide and have baseline data. This population is specifically defined for the 14-week placebo-controlled, double-blind period (Period 1). Analysis performed on PCS will be based on subjects as randomized.
- Per-Protocol Set at End of Period 1 (PP at EOP1): All subjects in PCS without any major protocol violations that will result in exclusion of the subjects from the analysis.
- Per-Protocol Set at End of Period 2 (PP at EOP2): All subjects in FAS without any major protocol violations that will result in exclusion of the subjects from the analysis.
- Completers Set (CS): all subjects in the PP at EOP1 population who continue on active treatment or placebo to complete a full 14-week placebo-controlled double blinded period (Period 1)

The FAS population is the primary population for the analysis of efficacy endpoints. The DUS population may be used for sensitivity analyses of efficacy endpoints, as appropriate.

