The SA Set is the primary population for the analysis of safety endpoints.

The following analysis sets may be used for supportive/exploratory analyses (note that in the following exploratory analysis sets, if a patient's height at the primary endpoint timepoint,

i.e., ~Week 53 visit, is not available, then the last available measurement of height will be used to define the analysis sets).

[figure not shown]

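### SAP 1.1.1 limits the safety conclusions, as well as efficacy, to the 38 pivotal patients, so dosed supplemental patients are left out by default

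*SAP*

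**What the plan says.** SAP 1.1.1 describes two groups of patients. It records that "a cohort of the supplemental patients was added into the protocol in the midcourse of the study" and fixes the pivotal group by enrolment order: "a total of 38 patients (the first 32 BBS patients and 6 AS patients) will make up the pivotal cohort". It then sets the scope of reporting. The sentence opens "All analyses for CSR and Submission, including demographics, disposition, baseline characteristics, efficacy, and safety etc., will be performed" and goes on to give their basis: they "will be performed and the conclusions will be drawn based on the data from the pivotal cohort of patients". A general default follows: "unless stated otherwise, all analyses in the SAP refer to pivotal cohort only". The reason given for the other group is short: "The purpose of the supplemental cohort is to gain more treatment experience".

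SAP 2.1 defines the Safety Analysis Set as "All patients who received at least 1 dose of study drug (placebo or setmelanotide"), analysed by treatment received, and adds: "The SA Set is the primary population for the analysis of safety endpoints". The definition mentions neither cohort. Protocol 8.2 defines the set in the same way and has no pivotal/supplemental split. Protocol 4.1 allows enrolment beyond the planned 30 or so, without giving a number. SAP 1.1.1 also says that the SAP prevails over the protocol where the two differ.

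The only visible place where the cohorts may be combined is SAP 3.8.2, for paediatric subgroup analyses of efficacy endpoints, because the pivotal paediatric numbers may be small.

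**The concern.** A fixed pivotal cohort has a clear purpose for efficacy: it stops the tested population from changing after the fact. That purpose does not carry over to safety. No safety hypothesis is visible in either document, and adding exposed patients to a safety summary cannot affect the type I error of the efficacy test.

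In an ultra-rare disease the number of people ever exposed is small, and the supplemental cohort exists to enlarge experience with the treatment. Harms are a main part of that experience. Under the stated default, a serious event in a supplemental patient would not appear in the tables on which the safety conclusions rest.

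There is also a practical problem. SAP 2.1 does not repeat the cohort limit, so it is unclear whether a set of all dosed patients counts as an exception to the default. Two programmers could build different safety sets from the same text.

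**Working it through.** **Inputs**

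- Pivotal cohort, SAP 1.1.1: 32 BBS + 6 AS = 38. The stated total reproduces.
- Supplemental patients dosed: not given in either document. Assumed here as 6, 10 or 20, for totals of 38 + 6 = 44, 38 + 10 = 48 and 38 + 20 = 58.
- The documents state no safety sample size or detection probability, so there is no safety figure of theirs to reproduce.

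**Formulas**

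- Exact one-sided 95% upper bound with zero events in N patients: 1 − 0.05^(1/N). For N = 38: 1 − 0.05^(1/38) = 0.0758.
- Chance of at least one case at true incidence p: 1 − (1 − p)^N. For N = 38 and p = 0.03: 1 − 0.97^38 = 0.686.

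**Results**

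| N | Basis | Zero-event upper bound | At least one case, p = 1% | At least one case, p = 3% |
|---|---|---|---|---|
| 38 | pivotal only | 7.6% | 31.7% | 68.6% |
| 44 | assumed +6 | 6.6% | 35.7% | 73.8% |
| 48 | assumed +10 | 6.1% | 38.3% | 76.8% |
| 58 | assumed +20 | 5.0% | 44.2% | 82.9% |

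These rows treat every added patient as exposed to setmelanotide and as fully observed as a pivotal patient, so they are upper limits on the gain. Suppose that 10 supplemental patients were randomised 1:1 and that the 5 on placebo had not crossed over by the cut; the documents do not say whether this would be so. The exposed total would then be 38 + 5 = 43 and the bound 6.7%, against 6.1% at 48. Shorter follow-up would reduce the gain further for harms that take time to appear.

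**Reading the sections together.** SAP 1.1.1 names safety and sets a default that yields only to an express exception. SAP 2.1 words the Screening Analysis Set, the Safety Analysis Set and the FAS alike, as all patients meeting a condition. If that wording does not lift the default for the FAS, it need not lift it for the Safety Analysis Set. The natural joint reading is all dosed patients within the pivotal cohort. SAP 3.8.2 shows how the authors write an exception when they intend one: they name both cohorts. SAP 2.1 does not.

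**The case against.** Four arguments stand against the point.

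1. *A reader might infer that SAP 1.1.1 and SAP 2.1 contradict each other.* The documents do not support that. The default in 1.1.1 governs the definitions that follow, and the two sections are compatible as set out above. What remains is an ambiguity about which cohort the set covers.

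2. *A reader might infer that supplemental safety data are thrown away.* That is also not supported. Protocol 9.8 requires case report forms, including adverse events, for every study patient. SAP 3.10 puts recorded CRF data into listings with the study report; whether the pivotal-only default limits those listings is not stated. SAP 3.12 allows further data cuts for submissions, shaped by regulators' requests. In addition, the SAP text available runs from 4.3.4 straight to 4.7, and the body of Protocol 8.6 is not visible. An exception for safety could stand there, and text that is not visible is not a fault of the plan. The point therefore rests only on the visible rule, which names both safety and the conclusions.

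3. *The size is unknown.* This stands. The supplemental number is an assumption, and the gain is modest at the lower end.

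4. *Adding supplemental patients by treatment received could unblind.* This stands too. SAP 1.3.2 keeps assignments concealed until all randomised participants have finished Periods 1 and 2. If supplemental patients are randomised and still in those periods at the cut, a by-arm table could reveal assignments. The fix has to allow for it.

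Pivotal-only main tables, in a fixed cohort with mature follow-up, are a coherent choice. That is a reason to keep them, but not to leave every other dosed patient out of the safety conclusions.

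**Conclusion.** The point holds in limited form. By an express rule in SAP 1.1.1, supplemental patients dosed under this protocol fall outside the safety analyses and safety conclusions by default, and no visible text reverses that for safety. SAP 2.1 leaves the cohort of the Safety Analysis Set unstated.

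On the 38 pivotal patients, zero events would leave an incidence of up to 7.6% compatible with the data (one-sided 95%). Adding supplemental patients would lower this to between 6.6% and 5.0% for assumed additions of 6 to 20, and by less where follow-up is short or exposure was to placebo only. Even a total of 58 would have only a 44.2% chance of showing a 1% harm. The case therefore does not depend mainly on these figures: whatever the cohort's size, one serious event in one supplemental patient should be able to inform the safety conclusions.

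The primary result is untouched. This is a low-cost improvement to the safety reporting, not a flaw in the efficacy analysis.

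**What to change.** - In SAP 1.1.1, keep the pivotal-only restriction for efficacy and keep the planned pivotal safety tables. Add a safety summary (adverse events, serious adverse events, discontinuations) of all dosed patients, pivotal plus supplemental, up to the data cut. Require the safety conclusions to take it into account.
- In SAP 2.1, state which cohort each safety table uses.
- Give exposure-adjusted rates in the added summary, because follow-up will differ between the cohorts.
- Pool over randomised arms for any supplemental patient whose assignment is still blinded at the cut.

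The cost is a small set of extra tables and the cleaning of supplemental safety data for the cut. The added patients will have shorter follow-up, and there can be no by-arm split for them until they are unblinded. No efficacy analysis changes.

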1.2. Study Objectives

A brief note of initial clarification: as outlined in more detail in Sections 1.3.1 and 3.10.1, the nature of the study design includes a randomized, double blinded and placebo-controlled 14-week Period 1, followed directly by a \sim 38 weeks open label, active treatment Period 2, resulting in \sim 52 weeks on therapy. Patients then continue into another 14 weeks longer-term treatment. However, the primary analysis is planned after the last enrolling patient has finished Period 2 (i.e., at the end of \sim 52 weeks of overall therapy (placebo and/or active).

The approach to the primary analysis (i.e., main analysis for New Drug Application [NDA] filing or applications in other regulatory agencies as appropriate) is outlined in Section 4.3.1.

Taking into account that enrollment has been ongoing for some time, many patients will be well into their second year of treatment at the time the primary analysis is planned (as the last patient ends ~52 weeks of overall therapy on the study). Thus, it is anticipated only a small percentage of patients who are initially randomized into the placebo arm may have less than ~52 weeks of setmelanotide treatment by the timing of the primary analysis (end of Period 2)

for NDA or other regulatory filings.

1.2.1. Primary Objective

The primary objective of the study is to assess the effect of setmelanotide on the proportion of patients (\geq 12 years of age at baseline) treated for \sim 52 weeks who achieve a clinically meaningful reduction from baseline (i.e., \geq 10%) in body weight.

1.2.2. Secondary Objectives

The key secondary objectives of the study are to:

- Assess the effect of setmelanotide on mean percent change from baseline in body weight (in patients ≥12 years of age at baseline) after ~52 weeks of treatment.
- Assess the effect of setmelanotide on the mean percent change from baseline in the weekly average of the daily hunger score (in patients ≥12 years of age at baseline) after ~52 weeks of treatment.
- Assess the effect of setmelanotide on the proportion of patients who achieve a ≥25% improvement in the weekly average of the daily hunger score (in patients ≥12 years of age at baseline) after ~52 weeks of treatment.

Other secondary objectives of the study are to:

- Assess the effect of setmelanotide on the mean percent change from baseline in body weight (in patients ≥12 years of age at baseline) at the Week 14 visit compared with placebo.
- Assess the effect of setmelanotide on the mean percent change from baseline in the weekly average of the daily hunger score (in patients ≥12 years of age at baseline) at the Week 14 visit compared with placebo.

1.3. Study Design

1.3.1. Synopsis of Study Design

[figure not shown]
This is a pivotal study to confirm the long-term (approximately 1 year in most patients) efficacy and safety of setmelanotide treatment in patients who have BBS or AS.

The study will consist of 3 treatment periods (see Figure 1). After obtaining informed consent, potential patients will be screened to determine study eligibility. Eligible patients will enter a 14-week, randomized, double-blind, placebo-controlled treatment period (Period 1) that will be followed by a 38-week open-label treatment period (Period 2) in which all patients will receive setmelanotide. The primary analysis will be performed after the last patient enrolled has completed Period 2. To maintain the blind through Period 2, dose escalation to a fixed dose of 3 mg will be performed during the first 2 weeks in both the double-blind (Period 1) and 38-week open-label (Period 2) treatment periods. Following Period 2, patients will continue to receive open-label setmelanotide for 14 weeks (Period 3) after which they may be enrolled into a separate treatment extension study.

Patients will be randomized in a 1:1 ratio, stratified by age group (≥12 years or <12 years) and disease (BBS or AS), to receive either setmelanotide QD or placebo QD via SC injection for the first 14 weeks. Patients who are ≥16 years of age will start on setmelanotide 2 mg or matching placebo during the 2-week dose escalation and will increase to 3 mg or matching placebo at the beginning of Week 3. Patients who are <16 years of age will start on setmelanotide 1 mg or matching placebo during Week 1, will increase to 2 mg or matching placebo at the beginning of Week 2, and will increase to 3 mg or matching placebo at the beginning of Week 3. During the 14-week double-blind treatment period, patients will be evaluated at the beginning of Weeks 2 (telephone call only, patients <16 years old), 3, 7, 11, and 15 as depicted in Figure 1.

After the initial 14-week double-blind treatment period (Period 1), all patients will immediately transition to receive open-label setmelanotide QD via SC injection for 38 weeks (Period 2). To preserve the blind, all patients will be re-escalated to the 3 mg clinical dose. Thus, beginning at Week 15, patients who are ≥16 years of age will receive open-label setmelanotide 2 mg for 2 weeks, followed by a dose increase to 3 mg beginning at Week 17, and patients who are <16 years of age will receive open-label setmelanotide 1 mg during Week 15, 2 mg during Week 16, and 3 mg beginning at Week 17. Patients will be evaluated at the beginning of Weeks 16 (telephone call only, patients <16 years old) and 17 and then every 6 weeks thereafter during this Period 2. In Period 3, patients will be evaluated every 7 weeks.

Figure 1 Study Design Schematic

1.3.2. Randomization Methodology

This study will be open label, except for a 14-week double-blind, placebo-controlled period.

Patients who qualify for the study will return to the site on Day 1 of the double-blind period. Prior to randomization, the Investigator will ensure that the patient continues to meet inclusion and exclusion criteria. Patients who continue to be eligible to participate in the study will be assigned a unique randomization number based on a randomization code that will be generated prior to the start of the study. The randomization number codes the patient's initial treatment assignment (for the double-blind period) to either setmelanotide or placebo. The randomization scheme will randomize patients in a 1:1 ratio, stratified by age group (≥12 years or <12 years) and disease (BBS or AS), to receive either setmelanotide or placebo during the first 14 weeks of the study. Randomization numbers will not be re-used once assigned. Please refer to the official randomization plan for greater details.

The Investigator, study site staff, clinical research organization staff providing site management, and Medical Monitor will not have access to the actual treatment assignment administered during the 14-week double-blind, placebo-controlled treatment period (Period 1) except in the case of an emergency until all randomized participants have completed both the 14-week double-blind, placebo-controlled period and the 38-week open-label portion of the study (Period 2).

1.3.3. Stopping Rules and Unblinding

This study may be prematurely terminated, if in the opinion of the Investigator (at a participating site) or Rhythm (for the whole study), there is sufficiently reasonable cause. The terminating party will provide written notification documenting the reason for study termination to either the Investigator or Rhythm.

Circumstances that may warrant termination include, but are not limited to:

- Determination of unexpected, significant, or unacceptable risk to subjects
- Failure to enter subjects at an acceptable rate
- Insufficient adherence to protocol requirements
- Insufficient complete and/or evaluable data
- Plans to modify, suspend, or discontinue the development of the study drug

Rhythm Pharmaceuticals, Inc. Statistical Analysis Plan, Protocol RM-493-023 29 October 2020, Version 3.0

Should the study be closed prematurely, all study materials must be returned to the Sponsor or designee.

Every attempt will be made to maintain the blind through the end of the 38-week, open-label treatment period (Period 2) (i.e., until the database snapshot prior to completing the primary analysis). Breaking the blind for a patient should be done only in the event of a medical emergency where the identity of study drug is necessary to appropriately treat the patient. The Primary Investigator will be provided with access to a system to unblind their patients, but if possible, the decision to break the blind should first be discussed with the Medical Monitor. If the blind is broken, the reason, when, and how the blind was broken will be documented.

1.3.4. Study Procedures

The schedule of assessments (SOA), as outlined in the study protocol, is provided in Table 1 - Table 2.

Table 1 Schedule of Assessments: Screening through Week 53 Visit (End of Period 2)

Visit Escalation SET of PBO SET Escalation SET of PBO VIO V11 V12 V13 V12 V13 V13 V14 V14 V15 V15			Double-Blind Treatment (Period 1)			38-Week Open-Label Treatment (Period 2)										
Study Week -3* 1 2 3 7 11 15 15 17 23 29 35 41 47 53 Study Day (n/a) 1 8 15 43 71 99 106 113 155 197 239 281 323 365 Inclusion/exclusion review X X X Image: Comprehensive scince of the stronge of the st		Screening Visit				SET o	r PBO	SET	Escala	tion			5	SET		
Study Day (n/a) 1 8 15 43 71 99 106 113 155 197 239 281 323 365 Inclusion/exclusion review X	Visit (V) Number		V2		V3											
Informed consent/assent X X X X X X X X X X X X X X X X X X X			1	2												
Inclusion/exclusion review			1	8	15	43	71	99	106	113	155	197	239	281	323	365
Medical history review X Genetic testing¹ X Archive sample for storage² X Comprehensive skin exam³ X Fitzpatrick scale X Pregnancy test⁴ X X X† Study drug administration/dispense⁵ X X X Daily hunger questionnaire³ X																
Genetic testing¹			Х													
Archive sample for storage ²	Medical history review															
Comprehensive skin exam³ X Image: skin exam³ X Image: skin exam³ X X Image: skin exam³ X X X Image: skin exam³ X <	Genetic testing ¹	X														
Fitzpatrick scale	Archive sample for storage ²		Х					X†								X†
Pregnancy test⁴ X X† X <t< td="">Comprehensive skin exam³	X															</t<>	Comprehensive skin exam ³	X														
Study drug administration/dispense ⁵ X X X X X X X X X X X X X X X X X X X	Fitzpatrick scale	X	Х													
Daily hunger questionnaire ⁰ X ◄ Daily†	Pregnancy test ⁴	X	Χţ		Χţ	X†	X†	X†		Χţ	Χţ	Χţ	X†	Χţ	Χţ	X†
	Study drug administration/dispense ⁵		Х		Х	Х	Х	Х		Х	Χ	Х	Х	Х	Х	X
	Daily hunger questionnaira®	V							Dai	lu+						Į
Global fluinger assessments			•		V+	1		V+	— Dai			V+				V+
	Clobal hungar accomments															
	Global hunger assessment ^g	Х			7.			Λ		Λ		A				
	Global hunger assessment⁰	X			Λ			Λ		^1		A				
	Global hunger assessment [©]	X			~			A		A		A				
	Global hunger assessment [©]	X			7			A		A		A)				
	Global hunger assessment⁰	X			7			*		A)		A				
	Global hunger assessment®	X			7			*		*		A				,
	Global hunger assessment®	X			7			*		*		A				
	Global hunger assessment⁰	X			7.			 		*		A				
	Global hunger assessment⁰	X			A			 		X		A				
	Global hunger assessment⁰	X			70			 		*		A				

	Screening Visit	ı		Blind T Period	reatmer 1)	it.			38-V						
			T or Pl		SET	r PBO	SET	Escala	tion			5	SET		
Visit (V) Number	V1	V2		V3	V4	V5	V6		V7	V8	V9	V10	V11	V12	V13
Study Week	-3*	1	2	3	7	.11	15	15	17	23	29	35	41	47	53
Study Day	(n/a)	1	8	15	43	71	99	106	113	155	197	239	281	323	365
Concomitant medications review	Х	X	X.	Х	Х	х	X	Х	Х	Х	Х	X	Х	Х	Х

- Due to the rarity of these patients and difficulty associated with travel to the study site, the screening period may be extended beyond 3 weeks if necessary, after discussion with the sponsor.
- Assessment sample should be performed/obtained prior to administration of study drug.

 A blood sample will be obtained at Screening to confirm a genetic diagnosis of AS or BBS. However, patients may be entered into the study based on clinical diagnosis of BBS (≤10% of BBS patients) or prior genetic diagnosis of BBS (≥90% of BBS patients) or AS (100% of AS patients) (refer to Section 4.2). The DNA will not be studied or "typed" for any other purpose, unless patients are re-consented.
- 2 Extra retain samples will consist of 2 serum and 2 plasma (K2EDTA) vacutainer tubes and two 5ml urine tubes.
- A comprehensive skin evaluation will be performed by a dermatologist. Any concerning lesions identified thring the screening period will be biopsied and results known to be benign prior to first dose of setmelanotide. If the pre-treatment biopsy results are of concern, the patient will be excluded from the study.
- 4 A urine pregnancy test may be performed in order to expedite availability of results prior to dosing on Day 1. All other pregnancy tests will be serum; dosing may continue with results pending.
- 5 Patients/caretakers will draw up and self-administer/administer the drug once daily in the morning beginning the morning of Day 1 and for the duration of dosing. On days with clinic visits, the patients/caretakers will administer the drug in the clinic in the presence of the clinical staff to assure proper technique. Patients/caretakers will return all used vials to the clinic when they visit (the number recorded) and both clinic administered study drug, as well as outpatient study drug administration will be recorded in a

Daily hunger questionnaire scores will be recorded on a daily basis, prior to the patient's morning meal. If the patient is unable to assess their own hunger due to impaired cognitive function, a parent/caregiver assessment of hyperphagia (PWS-FPD) will be completed instead (see Appendix 11 5 2). During the Screening Period, the patient must complete the daily hunger questionnaire in the electronic diary at least four of the seven days prior to V2. Subjects who do not meet this requirement should not be randomized into the study. V2 may be rescheduled if needed to fulfill this requirement.

Rhythm Pharmaceuticals, Inc. Statistical Analysis Plan, Protocol RM-493-023 29 October 2020, Version 3.0

[figure not shown]
9 Global lunger questions (Appendix 11-5) will be asked an Screening, and Questions I and 2 will then be asked as specified in the SOA once doing has been initiated (Day 1). The Parent Caregiver Global Hunger and the should be used when the patient is unable to assess their own hunger.

Table 2 Schedule of Assessments: 14-Week Open-Label Treatment (Period 3) and Early Termination Visit

	14-Week Open-I (Peri	Label Treatment od 3)	
Visit Number (V)	V14	V15 (EOS)	
Study Week	60	66	Early Termination
Study Day	414	462	Visit
Archive sample for storage ¹		Χţ	
Comprehensive skin exam ²		Х	Х
Fitzpatrick scale		X	Х
Pregnancy test ³	Χţ	X†	X†
Study drug administration/dispense4	X	X	
Daily hunger questionnaire7	← Dai	ily† ——→	Х
Global hunger assessment ⁸		X†	X†
Concomitant medications review	Х	X	X
Nutritional counselling and monitoring		X	

[†] Assessment/sample should be performed/obtained prior to administration of study drug.

¹ Extra retain samples will consist of 2 serum and 2 plasma (K2EDTA) vacutainer tubes and two 5ml urine tubes.

